10.3.2.2 Concomitant Medications

If the start date of a medication is missing, the medication will be considered to have started prior to the study. Such a medication may also be considered concomitant, depending on the stop date or lack thereof. If the stop date of a concomitant medication is missing, then the medication will be treated as ongoing. If the start date of a medication is missing, the stop date will be used to determine whether or not it is concomitant. Medications with other incomplete start dates or end dates will be imputed as follows:

Incomplete medication start date/time:

- If only have a YEAR, impute as Jan. 1.
- Else if only have YEAR and MONTH, impute as Day 1 of month.
- Otherwise missing, no imputation.

Incomplete medication end date/time:

- If only have a YEAR, impute as December 31.
- Else if only have YEAR and MONTH, then impute to last day of the month.
- Otherwise missing, no imputation.

10.4 Primary Analyses

The primary analyses will be conducted when all subjects complete Week 12 of study treatment and the study and the data has been frozen for analysis.

10.5 Multicenter Considerations

This is a multicenter trial in the United States. Data from all study centers will be pooled for efficacy and safety analyses. Because the number of subjects at each center is likely to be small, no analyses will be performed by center.

10.6 Multiple Comparisons, Multiplicity

This Phase II study is exploratory in nature and no adjustment for multiplicity is planned. The existence of multiplicity is acknowledged and interpretation of the primary and secondary analysis results will be interpreted with caution.

10.7 Active-Control Studies

The placebo group will serve as a comparator in the primary analysis of this study.

10.8 Examination of Subgroups

Subjects will be categorized into the following common subgroups for the purposes of evaluating the primary and secondary efficacy endpoints. Due to the small sample size, subgroups will be summarized descriptively in place of subgroup analyses.

- Screening DHEAS ($\leq 1.2 \times \text{ULN}$; $> 1.2 \times \text{ULN}$)
- Inclusion Criteria #3: “DHEAS level $>$ age-matched reference ULN at the screening visit.” (Subjects enrolled into the study fully compliant with inclusion/exclusion criteria; subjects who marginally do not meet inclusion criteria #3)

11 STUDY SUBJECTS

11.1 Subject Enrollment and Disposition

11.1.1 Screened Subjects

Screening and disposition will be summarized by investigator as well as by treatment group (if randomized) and overall.

The percentages will be based on total subjects who screened for the study. A subject listing will be provided with the above information, as well as site ID, date of informed consent, and reason for screen failure for subjects who were screened but not randomized.

11.1.2 Randomized Subjects

Enrollment and disposition of randomized subjects will be summarized by investigator as well as by treatment group and overall.

A listing of disposition will be provided for all randomized subjects. A separated listing will present subjects who are excluded from ITT, mITT, or SAF analysis sets, along with reasons for the exclusions.

11.2 Protocol Deviations

Protocol deviations will be listed by deviation type (e.g., major) and category (e.g., noncompliance with study procedures or restrictions). All deviations will be identified prior to database freeze and will be summarized and presented in listing(s); listings will include flags for deviation type (major or minor). Major protocol deviations are defined per *Guideline for Industry: Structure and Content of Clinical Study* from (ICH E3) guidance. Major analysis protocol deviations include, but not limited to:

- Randomized subjects who did not satisfy efficacy inclusion and exclusion criteria,
- Randomization error,
- Subjects who received the wrong tildacerfont dose,
- Subjects who received prohibited concomitant medication(s),
- Subjects who are less than 80% compliant with aggregate study treatment

All protocol deviations will be summarized by deviation category and type. In addition, a listing of all deviations and major protocol deviations will be provided. Prior to locking the database, all protocol deviations will be reviewed and a remedy plan will be added as a note to file to adjust the efficacy analyses, as necessary.

11.3 Demographics and Baseline Characteristics

Demographics and baseline characteristics will be summarized and listed for all randomized subjects (ITT).

11.3.1 Demographics

Demographic characteristics will include age, age category (18 - 35 years, 36 - 40 years, and 41+ years), child-bearing potential, race, and ethnicity. Demographic characteristics will be summarized by randomized treatment group and overall. A subject listing of demographics will be provided.

11.3.2 Screening and Baseline Characteristics

The following screening characteristics include screening serum DHEAS and screening DHEAS category ($\leq 1.2 \times \text{ULN}$; $> 1.2 \times \text{ULN}$). The following baseline characteristics include baseline weight, height, BMI, and hormones (DHEAS, A4, ACTH, 17-OHP, 17-OHP category [$< 200 \text{ ng/dL}$; $\geq 200 \text{ ng/dL}$], and cortisol). Screening and baseline characteristics will be

summarized by randomized treatment group and overall. A subject listing of screening and baseline demographics will be provided.

11.4 Medical History

Medical history will be summarized by randomized treatment group and overall. Individual subject listings will include subject identification number and randomized treatment for all randomized subjects (ITT).

General medical history, be mapped to preferred terms and system organ classes using the Medical Dictionary for Regulatory Activities (MedDRA®) Dictionary (version 24.1). General medical history will be summarized by system organ class (SOC) and preferred term (PT). A subject listing of general medical history will include start date/end date, verbatim medical history term, SOC, PT, and ongoing status.

12 STUDY DRUG AND OTHER MEDICATIONS

12.1 Exposure to Study Drug and Study Treatment Compliance

Summaries of study drug exposure and compliance will be summarized overall and separately for each dose level of the Treatment Period. The source for study drug dosing and compliance is drug accountability.

The summaries will include the total number of doses taken, mean daily dose (mg/day), duration (days) of exposure, and study drug compliance (see definitions in [Section 9.3.13.1](#)) by treatment group. A subject who received multiple dose levels of tildacerfont will be included in each of the dose levels for the purpose of summarization.

The drug accountability information, including number of tablets dispensed, number of tablets returned, and number of tablets lost or destroyed, along with all summarized variables, will be listed in subject listings.

12.2 Prior and Concomitant Medications

All medication verbatim terms reported on the electronic case report form (eCRFs) will be mapped according to the World Health Organization (WHO) Drug Dictionary (WHO D Global-

B3 Sep2021). The medications will be mapped to Anatomical/Therapeutic/Chemical (ATC) class and preferred names.

Prior and concomitant medications (see definition in [Section 9.3.14](#)) will be summarized using WHO DD ATC class and preferred name. The summary results will be presented by treatment/dose level and overall. Prior medications will be summarized by randomized treatment group and overall. Concomitant medications will be summarized by treatment group and overall.

These summaries will present the number and percentage of subjects using each medication. Subjects may have more than one medication within an ATC class and preferred name. At each summary level subjects are counted once if they reported one or more medications at that level. Each summary will be ordered by descending frequency of incidence of ATC class and preferred name within each ATC class.

All medications will be provided in a subject listing with flags indicating study drug dose level. The variables include, but are not limited to: Start date/end date/ongoing, medication name, ATC class and preferred name, indication, dose, unit, form, frequency, and route.

13 EFFICACY ANALYSES

The efficacy analyses are planned after all subjects have completed the 12 weeks of randomized, double-blinded study treatment and the database is frozen. During the 12 weeks of double-blind, placebo-controlled treatment period, the tildacerfont group will escalate doses at Week 4 and Week 8 to 100 mg QD and 200 mg QD, respectively. The scheduled visits included in this treatment period include Day 1 (baseline), Week 4, Week 8, and Week 12. The primary efficacy analysis will compare individual tildacerfont dose groups to the placebo group with respect to the change from baseline in serum DHEAS.

These efficacy analyses will be performed using the mITT Analysis Set ([Section 8.2](#)) as the main analyses. The endpoints identified in [Table 1](#) as the primary efficacy endpoint ([1.1](#)), secondary efficacy endpoint ([2.1](#)), and exploratory efficacy endpoints ([3.1](#), [3.2](#), [3.3](#), [3.4](#), [3.5](#), [3.6](#), [3.7](#), [3.8](#), [3.9](#)) will be analyzed.

13.1 Primary Efficacy Analysis

The primary objective of the study is to evaluate the effect of tildacerfont on DHEAS levels in female adult subjects with PCOS who have elevated adrenal androgens at baseline over the 12-week, double-blind, placebo-controlled, dose-escalated Treatment Period.

13.1.1 Definition of Primary Estimand

The primary “treatment policy” estimand is the log-transformed change from baseline in serum DHEAS for the active arm (dose escalation of tildacerfont from 50 mg QD to 100 mg QD to 200 mg QD) compared against the matching placebo group after 12 weeks of double-blinded, placebo-controlled, dose-escalating treatment. The placebo treatment group will control for any potential placebo effects in PCOS subjects and their impact on the overall tildacerfont treatment effect. The superiority of tildacerfont is evaluated by comparing the change from baseline in the tildacerfont treatment group against the change from baseline in the placebo treatment group.

Population: The analysis population is the mITT analysis set, all PCOS subjects who were randomized into the study, received at least 1 dose of study drug (tildacerfont or placebo), have at baseline DHEAS assessment, and have at least one post-baseline DHEAS assessment.

Variable: The analysis variable is the log-transformed change in the serum DHEAS value from baseline at Week 12 for each treatment group and dose level. The change is calculated as the log-transformed Week 12 assessment subtracted by the log-transformed baseline value.

Intercurrent events: For the primary analysis, intercurrent events such as treatment interruption, treatment discontinuation, and use of prohibited medications will not be taken into consideration for analysis as we assume there are no clinically relevant anticipated intercurrent events in PCOS.

13.1.2 Statistical Hypotheses

For the primary efficacy endpoint, the null hypothesis for the treatment comparison is that there is no difference in change from baseline at Week 12 in DHEAS between tildacerfont and placebo

after the 12-week, double-blinded, placebo-controlled, dose-escalating Treatment Period. The alternative hypothesis is that there is a difference between a tildacerfont and matching placebo.

$$H_0: \mu_{tildacerfont} - \mu_{placebo} = 0;$$

$$H_A: \mu_{tildacerfont} - \mu_{placebo} \neq 0$$

Where $\mu_{tildacerfont}$ and $\mu_{placebo}$ are the tildacerfont and placebo group means of log-transformed change in the serum DHEAS.

13.1.3 Statistical Modeling and Testing

13.1.3.1 Analysis of Covariance

The normality of residuals will be evaluated (Section 10.2). If the distribution of residuals is judged non-normal, then the analysis will be repeated using rank values in place of the original values. Statistical testing for the exploratory efficacy endpoint will be performed using a (rank-based, if non-normal residuals) ANCOVA model. The model will comprise the (rank of, if non-normal residuals) log-transformed change from baseline value as the dependent variable; randomized treatment group (0 = placebo, 1 = tildacerfont) as a fixed effect; and the log-transformed baseline serum DHEAS and age as a continuous covariates. The estimation method for the ANCOVA model will be maximum likelihood.

The ranked value is obtained by ranking all non-missing ratio of post-baseline/baseline values, if a rank-based model is used. The formal testing for the group difference ($\neq 0$) between tildacerfont and placebo treatment groups in change from baseline will be conducted at the scheduled time point of Week 12 visit using the aforementioned ANCOVA model. Statistically significant difference will be declared if two-sided p-value < 0.05 .

The statistical model used to characterize the primary endpoint at Week 12 will also be used to characterize the tildacerfont response at earlier weeks, replacing the Week 12 outcome with the Week 8 and the Week 4 outcomes.

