Table 5	Pre-Specified Threshold Levels for ECG Parameters.....	42
Table 6	Study SPR001-210 Optional DHEAS Screening Visit (Protocol Version 6.1 December 6, 2022)	45
Table 7	Study SPR001-210 Schedule of Activities (Protocol Version 6.1 December 6, 2022).....	45
Table 8	Study SPR001-210 Clinical Laboratory Tests	49
Table 9	Study SPR001-210 Prohibited and Cautionary Concomitant Medications	50

List of Figures

Figure 1	Schema of Study SPR001-210 Study Visits	14
----------	---	----

List of Abbreviations and Definition of Terms

Abbreviation	Description
11KA4	11-ketoandrostenedione
11KT	11-ketotestosterone
11OHA4	11 β -hydroxyandrostenedione
11OHT	11 β -hydroxytestosterone
17-OHP	17-hydroxyprogesterone
A4	androstenedione
ACTH	adrenocorticotrophic hormone, corticotropin
ADaM	analysis data model
AE	adverse event
AESI	adverse event of special interest
BMI	body mass index
C-SSRS	Columbia–Suicide Severity Rating Scale
CDISC	Clinical Data Interchange Standards Consortium
CI	confidence interval
CSR	clinical study report
CTCAE	Common Terminology Criteria for Adverse Events
CV	coefficient of variation
DHEA	dehydroepiandrosterone
DHEAS	dehydroepiandrosterone sulfate
ECG	electrocardiogram
eCRF	electronic case report form
FDA	Food and Drug Administration
FSH	follicle-stimulating hormone
GM	geometric mean
GMR	geometric mean ratio
HR	heart rate
ITT	Intent to Treat (Population)
LH	leutinizing hormone
log	logarithmic function
LS	least squares
MedDRA	Medical Dictionary for Regulatory Activities
mITT	modified Intent to Treat (Population)
MMRM	mixed-model for repeated measures
PCOS	polycystic ovary syndrome
PK	pharmacokinetic

Abbreviation	Description
PP	per-protocol
PT	preferred term
QD	once daily
QTcF	Fridericia-corrected QT interval
REML	restricted maximum likelihood
RTSM	randomization and trial supply management
SAE	serious adverse event
SAP	statistical analysis plan
SDTM	standard data tabulation model
SHBG	sex hormone binding globulin
SUSAR	suspected unexpected serious adverse reaction
SOC	system organ class
TEAE	treatment-emergent adverse event
ULN	upper limit of normal
WHO DD	World Health Organization Drug dictionary

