1 REVISION HISTORY

Version	Date	Document Owner	Revision Summary
1.0	20MAR2023	[name]	First version
2.0	17MAY2023	[name]	Addition of subgroup analysis for the primary and secondary endpoints based on Inclusion Criteria #3; Added additional analysis of the primary endpoint using an MMRM model; Added supportive analyses of the secondary endpoint

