9.1 Presentation of Summary Statistics

For most summary statistics, data will be analyzed and displayed in tabular format.

Unless otherwise specified, continuous efficacy hormones ([Section 5.2.2.1](#)) will be summarized using a 11-point descriptive statistics (i.e., n, mean, standard deviation [SD], median, 25% quartile [Q1], 75% quartile [Q3], minimum, maximum, geometric mean, geometric coefficient of variance [CV%], 95% confidence interval [CI] for geometric mean [including geometric mean ratio and its 95% CI]).

All other continuous variables will be summarized using an 8-point descriptive summary (n, mean, SD, median, Q1, Q3, minimum, and maximum) unless otherwise specified.

The same number of decimal places as in the observed value will be presented when reporting minimum and maximum; 1 additional decimal place than in the observed value will be presented when reporting mean, median, Q1, Q3, geometric mean, 95% CI; 2 additional decimal places than in the observed value will be presented when reporting SD. Geometric CV% will be reported to one decimal place.

All categorical/qualitative data will be presented using the frequency of events and percentages. All percentages will be presented to 1 decimal place, unless otherwise specified. Percentages equal to 100 will be presented as 100% and percentages will not be presented for zero frequencies, with the exception of binary variables. For summaries of AEs and concomitant medications (CMs), the percentages will be based on the number of subjects who received study drug.

All analyses and summaries will be produced using SAS® version 9.4.

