13.1.4.2 Summary of Analysis Results

The p-value for testing the treatment effect from the (rank-based, if non-normal residuals) ANCOVA model will be reported. In addition, if the normality assumption holds, the back-transformed least squares (LS) GMR of change from baseline (post-baseline/baseline), two-sided 95% CI of the LS GMR, the back-transformed LS mean ratio difference between treatment group (i.e., tildacerfont/placebo), and 95% CI of the LS mean ratio treatment difference will be reported from the ANCOVA model. If the normality assumption does not hold, the difference of medians and its 95% CI will be reported. These values will be obtained from bootstrap method as the 50th percentile, the 2.5th percentile, and the 97.5th percentile, respectively, of the difference in group medians from 5000 bootstrap random samples drawn with replacement.

The p-value for testing the treatment effect from the (rank-based, if non-normal residuals) MMRM model will be reported. In addition, if the normality assumption holds, the back-transformed least squares (LS) GMR of change from baseline (post-baseline/baseline), two-sided 95% CI of the LS GMR, the back-transformed LS mean ratio difference between treatment group (i.e., tildacerfont/placebo), and 95% CI of the LS mean ratio treatment difference will be reported from the MMRM model.

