13.1.5 Subgroups

The above ANCOVA and MMRM analyses will be repeated for two separate subgroups: the subgroup of subjects who fully meet the inclusion criteria #3, and the subgroup of subjects that do not meet this criterion. Furthermore, the primary endpoint analyses will be descriptively summarized for the other subgroup(s) specified in [Section 10.8](#).

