15 CHANGES RELATIVE TO THE PROTOCOL-SPECIFIED ANALYSIS

The study intended to enroll up to 40 subjects but was discontinued early on the basis of a business decision made by the sponsor. Due to the resulting small sample size, the exploratory efficacy analyses described in Protocol [Section 8.3.4](#) are replaced with summaries of descriptive statistics.

The MMRM analysis introduced in [Section 13.1](#) of this SAP is not mentioned in the protocol. However, to avoid protocol amendment, inclusion of this analysis in the SAP – well in advance of the database lock – is meant to serve the same intent.

The secondary endpoint of 30% reduction from baseline in DHEAS is mentioned in the protocol and sections [6](#), [6.1.2](#), [9.3.12](#) and [13.2](#) of this SAP. However, since some subjects have entered the study up to 25% lower than anticipated DHEAS into the study, it is necessary to assess respond at lower threshold of reduction at 25% and 20% in addition to originally planned 30% reduction.

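### Maximum likelihood for the primary ANCOVA, with no degrees of freedom stated, gives a nominal 5% test a true size of 6.5% to 7.6% at 33 subjects, and more at smaller n

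*SAP*

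**What the plan says.** SAP Section 13.1.3.1 defines the primary analysis as an ANCOVA of log-transformed change from baseline in DHEAS at Week 12. The terms are randomized treatment, log baseline DHEAS and age. On fitting it says: "The estimation method for the ANCOVA model will be maximum likelihood". On the decision rule it says: "Statistically significant difference will be declared if two-sided p-value < 0.05".

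The same section reuses the model at Weeks 8 and 4 and gives a rank version for non-normal residuals. Section 13.1.5, part of the changes made in SAP version 2.0, extends it further: "The above ANCOVA and MMRM analyses will be repeated for two separate subgroups". These are the subjects who meet inclusion criterion 3 and those who do not.

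No section gives degrees of freedom, a reference distribution or a small-sample correction for this model. Section 9.1 fixes SAS 9.4 but no procedure. The term "restricted maximum likelihood" is in the list of abbreviations, but no section assigns it to a model. Section 15 records that the study "was discontinued early on the basis of a business decision made by the sponsor" and refers to a small sample size without stating it.

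**The concern.** For a linear model with independent normal errors, maximum likelihood and least squares give the same treatment estimate but different residual variances. Maximum likelihood makes no allowance for the mean parameters that were estimated, so its variance is biased downwards. In a large trial this does not matter. Here four parameters are fitted to at most a few dozen subjects.

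If the text is programmed as written, the primary p-value is too small, a true null is rejected more often than 5% of the time, and the model-based 95% interval is too narrow. The same holds wherever this ANCOVA is reused. In the non-normal branch the rank p-value is affected, but the bootstrap interval for the difference in medians (Section 13.1.4.2) is not.

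**Working it through.** **Inputs.** Mean parameters: intercept, treatment, log baseline DHEAS and age, so p = 4 (SAP 13.1.3.1). Two-sided alpha 0.05 (same section). Planned evaluable n = 33 at 2:1, and 39 after allowing for 15% dropout (Protocol 8.1, SAP 7). The achieved n is not given, so values below 33 are assumptions.

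**The plan's own figure.** A difference of 164 mcg/dL and SD of 154 at 2:1 give 11 + 22 = 33 subjects. Power is 82.2% by normal approximation and 79.8% by noncentral t on 31 df. 33/0.85 = 38.8, rounded up to 39. The sample size reproduces and is not affected by this point.

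**Standard error.** SE(ML) = SE(OLS) × √((n−4)/n). At n = 33, √(29/33) = 0.937, which is 6.3% too small. At n = 39, √(35/39) = 0.947, which is 5.3% too small.

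**Type I error.** Under the null with normal errors the least-squares statistic follows t on n−4 df exactly. Using the ML variance lowers the threshold that this statistic has to pass. The SAP does not say which reference applies, so the three natural ones are shown for n = 33:

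- t on n−4 df: 2.045 × 0.937 = 1.917, and 2·P(t₂₉ > 1.917) = 6.51%.
- Likelihood ratio: √(29 × (exp(3.841/33) − 1)) = 1.892, and 2·P(t₂₉ > 1.892) = 6.85%.
- Wald normal: 1.960 × 0.937 = 1.837, and 2·P(t₂₉ > 1.837) = 7.64%.

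| n | t, n−4 df | Likelihood ratio | Wald normal |
|---|---|---|---|
| 39 (no dropout) | 6.26% | 6.52% | 7.18% |
| 33 (planned evaluable) | 6.51% | 6.85% | 7.64% |
| 24 (assumed) | 7.14% | 7.72% | 8.87% |
| 18 (assumed) | 7.94% | 8.94% | 10.59% |
| 16 (assumed) | 8.36% | 9.63% | 11.54% |
| 12 (assumed) | 9.65% | 12.05% | 14.82% |

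With normal residuals, coverage of the 95% interval is 100% minus the t or normal entry: 93.5% or 92.4% at n = 33, and 93.7% or 92.8% at n = 39.

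**Simulation check.** With 60,000 null trials at n = 33 and normal errors, the rejection rates were 6.5% (t), 6.8% (likelihood ratio) and 7.6% (normal), against 4.98% for least squares with t on 29 df. For the rank version at n = 33 they were 6.5%, 6.8% and 7.6% with normal errors (30,000 trials; least squares 5.0%). With heavy-tailed t₃ errors they were 6.7%, 7.1% and 7.8% (40,000 trials; least squares 5.2%).

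**Subgroups.** The two inclusion-criterion-3 subgroups are complementary. With 33 evaluable subjects the smaller has at most 16, so where its model can be fitted with residual degrees of freedom the error is at least the n = 16 row. A subgroup of four or fewer leaves no residual degrees of freedom and no test.

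**The case against.** The strongest reply is that the SAP names an estimation method, not a variance divisor or a reference distribution. The 7.6% needs a normal reference that the SAP never mentions; with the t reference usual for an ANCOVA the excess is about 1.5 points. The protocol calls the model plainly an ANCOVA, SAP 13.1.4.2 speaks of least squares means, and the sentence sits in a paragraph that mislabels the primary endpoint as exploratory. It may be a slip, and a programmer who used least squares would have no excess. The study is also exploratory, has no multiplicity adjustment and promises cautious interpretation. Three unadjusted visit tests alone carry roughly an 8% to 12% chance of a false positive (assumed between-visit correlation 0.9 to 0.5). At n = 33 the conclusion changes only if the correct p-value lies between 0.050 and about 0.065 (t) or 0.076 (normal).

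Much of this stands as a limit on weight. It does not remove the point. Every natural reading exceeds 5%, including the most lenient. Least squares means can be taken from a maximum likelihood fit, so that wording does not settle the matter. Using least squares would depart from the written method, and SAP Section 4 makes the SAP govern over the protocol. Accepting multiplicity does not justify understated standard errors in each single test.

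Two qualifications are fair. The rates below n = 33 are scenarios and cannot set the severity. On subgroups, Section 10.8 says they will be described rather than analysed, which conflicts with 13.1.5. Section 13.1.5 is the more specific, ordering models for the criterion-3 subgroups and leaving description to the others, but the conflict should be resolved. The main point does not depend on it.

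**Conclusion.** The concern holds. As written, the primary test at nominal 5% has a true size of 6.5% to 7.6% at 33 evaluable subjects, depending on the unstated reference distribution. These figures assume normal errors, four mean parameters and implementation of maximum likelihood as stated. The direction at smaller n is certain; the size after the early stop is not, because the achieved n is not reported. The consequence is modest in an exploratory phase 2 study, but it affects the primary p-value and should be corrected.

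**What to change.** In SAP 13.1.3.1, replace maximum likelihood with ordinary least squares or, equivalently, REML with a t reference on n−p degrees of freedom. State that this applies wherever the ANCOVA is used: Weeks 12, 8 and 4, the rank version, and the inclusion-criterion-3 subgroup models if they are kept.

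Under normal errors this restores a size of exactly 5% at every n. In the rank version the size is approximate: simulated at 5.0% to 5.2% at n = 33, and 5.5% at an assumed n = 12 with t₃ errors.

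The cost is one phrase in the SAP before unblinding and one procedure setting, with no added model or test. Point estimates are unchanged. With a t reference before and after, intervals widen by √(n/(n−4)) − 1: 5.6% at n = 39, 6.7% at n = 33, and for assumed sizes 9.5% at n = 24 and 22.5% at n = 12.
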